Society: This research will test a promising drug intervention in the treatment of hypothalamic obesity. Furthermore, the proposed work will help us understand the biological mechanisms involved in the development of hypothalamic obesity. CP tumors are the *most common suprasellar tumors of nonglial origin* in children.¹³⁷ Severe obesity is a major risk factor for CP-related morbidity and mortality. The general public will benefit in a substantial way from an improved understanding of the etiology of obesity, and in particular of hypothalamic obesity, with the potential to lessen the burden on individual suffering as well as health care costs.

Adverse Events/Reporting

Investigator Oversight Responsibilities

Day-to-day oversight of the trial is provided by the Principal Investigators, Drs. [name] and [name]. Along with [name], Drs. [name] and [name] assure that informed consent is obtained prior to performing any research procedures, that all subjects meet eligibility criteria, and that the study is conducted according to the research plan approved by the three local IRBs (Seattle, St. Paul, Vanderbilt). Drs. [name], [name], and [name] will review all study data, all adverse events (AEs), and any serious adverse events (SAEs) in real-time. All SAEs and dose-limiting toxicities will be reported to the independent Data Monitoring Committee (DMC) and IRB according to the approved Data and Safety Monitoring Plan.

External monitoring for the study is provided by the Institute of Translational Health Sciences (ITHS) of the University of Washington, and includes regular onsite data monitoring and regular review by the DMC (5 members), and the study team (i.e. Principal Investigators and co-investigator).

Monitoring Procedures

Please see details outlined separate Data and Safety Monitoring plan for adverse events monitoring and reviewing as well as DMC meetings and reporting for this study.

Adverse events are identified during study visits when potential AEs are assessed by clinical history and by physical examination of the subject. Each study site will report AEs to their IRBs as well according to their IRB guidelines. In addition, all AEs are reported according to Seattle Children's Hospital IRB reporting guidelines.

Serious adverse events and dose-limiting toxicities are submitted within one day of learning of the event to the IDMC via the REDCap SAE reporting system. Serious adverse events will be listed by organ system using the Medical Dictionary for Regulatory Activities (MedDRA) system. Study data and study conduct reports are prepared by the study statistician and include accrual, drop-outs, protocol deviations, and AEs in aggregate. These reports, including safety lab measures, SAEs and dose-limiting toxicities will be provided to the IDMC and the study team on a semi-annual basis for review.

Monitoring Reports

The DMC provides a written report to the study team with recommendations for study modification, study continuation/discontinuation as relevant. The study team is responsible for forwarding the report to the IRB.

Performance, Safety, and Treatment Issues

A report will be generated semi-annually by the study statistician and submitted to the DMC and study team. This report will include performance information including participant recruitment and retention, study conduct, data collection, quality control, and completion, and protocol adherence. This report will also include safety information, including any adverse events or dose-limiting toxicities. The report will also include results from treatment integrity/fidelity assessments to ensure the adequate and consistent provision of treatment.

Collection and Reporting of SAEs and AEs

For this study, the following standard AE definitions are used:

Adverse event: Any unfavorable and unintended sign (including an abnormal laboratory finding), symptom or disease temporally associated with the use of a medical treatment or procedure, regardless of whether it is considered related to the medical treatment or procedure.

Serious Adverse Event: Any AE that results in any of the following outcomes:

- Death
- Life-threatening
- Event requiring inpatient hospitalization or prolongation of existing hospitalization
- Persistent or significant disability/incapacity

AE grading and attribution scale: As outlined in Data Safety and Monitoring Plan.

AE Management: See details in Data Safety and Monitoring Plan.

Emergency Unblinding. In case of drug-related SAEs and treatment-emergent adverse events (TEAEs) the Principal Investigators will be contacted immediately to contact the DMC (see data safety and monitoring plan) and consider the need to break the blind.

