Meal test. At study visits 1, 3 and 4 (0, 18 and 36 wk), subjects will have an OGTT (900-1100 AM) in the fasting condition, followed at study visits 0 and 36 wk by a standardized mixed meal caloric preload (macaroni & cheese at 1100 AM) and a free buffet meal (at 1230 PM). The buffet meal is an objective measure of satiety as it assesses food intake and choice after a caloric preload. The standardized test meal preload will provide 12% of estimated daily caloric requirements,⁸¹ based on the Schofield-HW equation.⁸² The purpose of the test meal is to ensure that study participants are in an equally fed state (together with oral glucose, total preload will be 22-27% of estimated daily caloric intake). Ninety minutes later, an ad libitum buffet meal will be served consisting of a wide variety of food items and more than the child's estimated daily calorie requirements will be offered (5,000 kcal). Participants will have access to the buffet for 30 min, after which calorie intake and composition of consumed foods will be measured by weighing back uneaten food. Hunger and fullness will be assessed every 30 min from fasting state before starting the OGTT until the end of the buffet meal using visual analog scales (VAS)⁸³ to assess subjective appetite, reliable in children over age 7 y,⁸⁴ and used by us previously.⁸⁵

Metabolic outcomes. Blood glucose, insulin, lipid panel, hemoglobin A1c, and as a measure of low-grade inflammation C-reactive protein will be assessed by high-sensitive (hsCRP) testing at a central lab (Northwest Lipid Research Laboratories, Seattle). Glucose tolerance will be assessed by a 2-hour oral glucose tolerance test. After placement of an intravenous catheter (IV), a baseline blood sample will be collected for measurement of hemoglobin A1C, and insulin (processed by the central lab). A 2-h OGTT (1.75 g/kg Glucola [maximum 75 g]) will then be performed with sample collection at 0', 30', 60', 90' and 120' for measurement of glucose and insulin. Samples will be placed on ice, and will be centrifuged. Leptin, total adiponectin, α -MSH, and soluble leptin receptor (sOB-R) are potential indicators of leptin sensitivity,⁸⁶⁻⁸⁹ and will be assessed in fasting state (leptin, total adiponectin, and sOB-R, R&D Systems, Minneapolis, MN; α -MSH, Phoenix Pharmac., Belmont, CA, the assay cross

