Table 1. Summary of Study Measures and Outcomes and Their Use in the Proposed Research

Measure	Domain	Instrument	Aim	Role/Application
$\Delta\text{BMI}\%$	Adiposity	Anthropometry	1	Primary outcome
Total body fat mass	Body composition	DEXA	1	Secondary outcome
Fat and total calorie intake	Post test meal satiety assessment	Free buffet meal analysis	1	Secondary outcome
Glucose tolerance	Glucose tolerance, MetS	Glucose at 0', 120' (OGTT)	2	Secondary outcome
HDL, triglycerides	MetS	Fasting lipids	2	Secondary outcome
hsCRP	Inflammation	hsCRP at fasting time point	2	Secondary outcome
Free living EE	Energy homeostasis	Doubly labeled water	3	Tertiary outcome
Energy intake	Energy intake	24h dietary recall (ASA24)	3	Tertiary outcome
Leptin, adiponectin, sOB-R, α -MSH, HOMA-IR, WBISI	Energy homeostasis, leptin sensitivity, and insulin resistance	Baseline and stimulated hormones	3	Tertiary outcomes and predictors

Aim 1: To test effects of GLP1RA on hypothalamic obesity prospectively.

Sample: Available anthropometry measures will be included in the analyses (see also Fig. 1 below).

Primary outcome analysis: For efficacy analysis the primary outcome is % change in BMI from week 0 (baseline) to 36 wk. A piecewise (separating the randomized and run out phases) linear mixed-effects model¹¹¹ will be fit with % change in BMI from baseline to 36 wk as the outcome; treatment, time, and the interaction between treatment and time as factors of interest; and randomization stratification variables (site, age, and gender) included as covariates. This model is a generalization of analysis of covariance (ANCOVA) that allows all follow-up repeated measures to be included.

Table 2. Additional Descriptive Parameters, Predictors and Covariates used in Study

Measure	Domain	Instrument	Aim
ΔBMI , ΔBMI z-score	Adiposity	Anthropometry	1
Subjective appetite	Hunger and fullness rating	Visual analog scale	1
Syst. & diast. BP	CVD risk factor, MetS	Ambulatory BP	2
Exercise	Physical activity measure	Actigraphy ^{112,113}	3
Energy intake	Energy intake	24h dietary recall	3
Eating behavior	Assessment of overeating and food reward	Overeating (CEBQ), ⁷⁶ & hyperphagia. ⁷⁷	3
Brain lesion score, hypothalamic region and residual lesion volumes	Structural lesion in the pituitary-hypothalamic area	Brain MRI images	3

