- Weight stable or increasing over 3 months prior to screening visit
- Stable hormone replacement for at least 3 months prior to screening visit

Exclusion Criteria

- Renal impairment (GFR<60 ml/min/1.73m² using the Schwarz formula¹¹⁶)
- History of gastroparesis; pancreatitis or gallstones (unless status post cholecystectomy)
- Family history of multiple endocrine neoplasia type 2 or familial medullary thyroid carcinoma metabolic disorders
- Any insulin-treated diabetes mellitus, poorly controlled type 2 diabetes (HbA1c $\geq 10\%$), or any other chronic serious medical conditions such as CVD, malignancy or hematologic disorder, complicated syndromic disorder, or psychiatric disorders (schizophrenia, major depression, history of suicide attempts)
- Calcitonin $>50 \text{ mg/L}$ at screening
- Initiation of weight loss medications within 3 months of screening visit
- Previous donation of blood $>10\%$ of estimated blood volume within 3 months prior study
- Current warfarin use
- Current use of any other GLP1RA
- Untreated thyroid disorder or adrenal insufficiency

- History of bariatric surgery or planned bariatric surgery until end of study
- Pregnancy, lactation or expectation to conceive during study period
- Subject unlikely to adhere to study procedures in opinion of investigator
- Subject with contraindication to neuroimaging by MRI

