Hyperglycemia: The oral glucose load (1.75 g/kg, max. 75 g) can lead to significant hyperglycemia. All patients will be screened for diabetes before the study will be started. Any patient that meets the criteria for diabetes mellitus will be excluded from the OGTT and referred to the diabetes outpatient clinic for treatment. Any subject with insulin-treated diabetes mellitus or poorly controlled type 2 diabetes will be excluded from the study (see exclusion criteria). If patients develop diabetes during the study, management will be coordinated with their primary endocrinologist.

Nausea and abdominal discomfort: Due to the transient nature of the abdominal discomfort and nausea related to the study drug, and in order to prevent self-imposed drug holidays, all patients who experience nausea or abdominal discomfort are asked to contact the study team. The PI at each site will personally discuss appropriate therapy for this self-limited side effect.

Meals: At weeks 0, 18 and 36, subjects will have an OGTT (9:00-11:00 AM) in the fasting condition, which will be followed at weeks 0 and 36 by a standardized mixed meal caloric preload (macaroni & cheese at 11:00 AM) and a free buffet meal (at 12:30 PM). The test meal (macaroni & cheese) will be followed by an ad libitum buffet meal will be served consisting of a wide variety of food items and more than 100% of the subject's estimated daily calorie requirements. Children will have access to the buffet for 30 min., after which calorie intake and composition of consumed foods will be measured by weighing back uneaten food. Subjects will be screened for food allergies and sensitivities. In addition, all meals will be prepared fresh by the Clinical Research Center Nutrition Research Kitchen, and stored under adequate conditions. Duration of fasting is limited to 9:00 AM, and subjects can have water.

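### Eligible subjects with diabetes have no OGTT, so they lack 120-minute glucose and reach the buffet with about half the planned preload; the plan does not say how either is analysed or whether the rule continues after randomization

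*Combined protocol and SAP*

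**What the plan says.** **Eligibility.** Among diabetes criteria, Section 5 (Exclusion Criteria) removes only "Any insulin-treated diabetes mellitus, poorly controlled type 2 diabetes", the latter meaning HbA1c at or above 10%. Other type 2 diabetes can be randomized.

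**OGTT restriction.** Section 7 (Methods to Minimize Risks, Hyperglycemia) first says "All patients will be screened for diabetes before the study will be started", then "Any patient that meets the criteria for diabetes mellitus will be excluded from the OGTT". It repeats the eligibility exclusions and adds: "If patients develop diabetes during the study, management will be coordinated with their primary endocrinologist". It does not say whether later OGTTs go ahead in a subject who becomes diabetic.

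**OGTT schedule.** Section 4 (Meal test) makes no exception: "At study visits 1, 3 and 4 (0, 18 and 36 wk), subjects will have an OGTT".

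**Outcomes.** Table 1 lists OGTT glucose at 0 and 120 minutes, and fat and total calorie intake at the buffet, as secondary outcomes. The Analysis section makes ITT the primary population for all of them.

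**Preload.** "The standardized test meal preload will provide 12% of estimated daily caloric requirements", and "together with oral glucose, total preload will be 22-27% of estimated daily caloric intake". The stated aim is that participants start the buffet equally fed. No substitute is described for a subject who does not take the glucose.

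**Missing data.** The Analysis section says only that the chosen methods can use partial data, and it names one sensitivity analysis, in completers. Diabetes status is neither a stratification factor nor a listed covariate.

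**The concern.** The safety rule and the outcome definitions were written in different sections and do not meet. Two secondary outcomes are affected.

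1. **120-minute glucose.** Subjects with diabetes at entry, whose glycaemia is likely to be among the highest, have no value at any visit and so no change score. WBISI and the insulinogenic index, which also need the OGTT, are lost with it. If the rule is also applied after randomization, a subject whose glycaemia worsens into diabetes loses the later value because of that worsening. This would happen more often in the arm with less benefit.
2. **Buffet intake.** A subject without the OGTT receives only the meal part of the preload. With diabetes at entry, preload differs between subjects. With diabetes arising on study and the OGTT then omitted, it also changes within a subject between weeks 0 and 36.

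The completer analysis does not address this, since such a subject can finish the study and still have no OGTT. Three sites could also apply the rule differently after randomization.

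**Working it through.** **1. The plan's own power figure.** Inputs from Section 4 (Aim 2): 19 evaluable per group, standardized effect 1, two-sided alpha 0.05, stated power 85%. For a two-sample t test the noncentrality is 1/√(2/19) = 3.08 on 36 degrees of freedom, which gives 85.1%. The figure reproduces and is not in error, but it allows for 20% dropout only and not for OGTTs withheld.

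**2. Precision lost to diabetes at entry.** The documents give no diabetes frequency, so the share is an assumption, taken as equal in both arms.

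| Share without OGTT (assumed) | Left per group | Power for 120-minute glucose, effect 1 SD |
|---|---|---|
| 0% | 19 | 85.1% |
| 5% | 18 | 83.0% |
| 10% | 17 | 80.7% |
| 20% | 15 | 75.3% |

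**3. Preload.** Oral glucose supplies 22 − 12 = 10 to 27 − 12 = 15 percentage points of daily calories. Without it the subject gets 12/27 = 44% to 12/22 = 55% of the planned preload. For the maximum load of 75 g, at an assumed 4 kcal/g, the shortfall is 75 × 4 = 300 kcal. At 1.75 g/kg the maximum is reached at 75/1.75 ≈ 43 kg.

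**4. Attenuation if the rule also applies on study.** Everything here is assumed. Let latent glycaemia at week 36 be N(0,1) on placebo and N(−d,1) on drug, correlated ρ with 120-minute glucose. A subject is excluded above the cut-off c that removes a fraction q of placebo. With λ(a) = φ(a)/Φ(a), the complete-case difference is

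d − ρ[λ(c) − λ(c + d)].

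Example with d = 1, q = 5%, ρ = 0.8: c = 1.645, λ(1.645) = 0.1086, λ(2.645) = 0.0121, so the difference is 1 − 0.8 × 0.0964 = 0.923, a shrinkage of 7.7%.

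| q (placebo) | Excluded on drug, d = 1 | Shrinkage for d = 1, ρ 0.6–0.8 |
|---|---|---|
| 5% | 0.4% | 6–8% |
| 10% | 1.1% | 10–13% |
| 20% | 3.3% | 16–22% |

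With 19 evaluable on placebo, 5% is one subject and 20% about four.

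**5. The same under a repeated-measures analysis.** Section 4 plans models that use all visits. A large-sample simulation used a missing-at-random analysis with weeks 0 and 18 observed, an assumed between-visit correlation of 0.5–0.7, and d = 1. If exclusion follows a high week-18 120-minute glucose, shrinkage is about 0%. If it follows an unobserved latent value with ρ = 0.8, shrinkage is roughly 4–5%, 6–10% and 11–16% at q = 5%, 10% and 20%. The complete-case figures in step 4 are therefore on the high side for the planned model.

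**The case against.** The strongest defence is that the OGTT restriction belongs to screening. It directly follows the sentence on screening before study start and is paired with referral to a diabetes clinic. Diabetes arising on study has its own sentence with a different action and no mention of the OGTT. On that reading OGTT exclusion is a pre-randomization feature. It cannot distort the comparison of arms, and an affected subject has the same reduced preload at weeks 0 and 36, so change in buffet intake compares like with like. This stands, and it is the more natural reading.

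Three stronger inferences are tempting, and the documents do not support them:

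- **That 120-minute glucose will be missing in the worst outcomes.** This needs the exclusion to continue after randomization, which the words allow but do not state.
- **That the glucose effect will be attenuated by a known amount.** No diabetes rate is given, and the planned model would recover some or all of the complete-case loss.
- **That buffet intake is biased upward in those without the glucose load.** No figure links the load to intake. It is taken at 9:00, and the buffet opens at 12:30 after the 11:00 meal. The documents show unequal preload, not the direction or size of its effect.

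It is also fair to say that Sections 5 and 7 do not contradict each other on eligibility. The gap lies between the OGTT restriction, the subjects that Section 5 admits, and the OGTT and preload that Section 4 assumes for everyone. The defence does not close that gap.

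**Conclusion.** The point holds in a limited form. On either reading, any subject randomized with diabetes lacks 120-minute glucose in an outcome declared ITT and gets 44–55% of the intended preload, contrary to its stated purpose. The cost is precision (about 2–3 points of power for each further 5% of subjects, at an effect of 1 SD) and coverage of the population, not bias between arms.

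Outcome-dependent missingness and a within-subject change in preload arise only if the exclusion extends to diabetes found after randomization. The size is then not determinable from the documents. About 6–22% complete-case shrinkage of a 1 SD effect corresponds to assumed placebo exclusion of 5–20% and correlations of 0.6–0.8, and the planned model would probably show less. The primary outcome, percent change in BMI, is unaffected. The change is worth making because it is cheap and needs no new data.

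**What to change.** 1. Reconcile the Hyperglycemia paragraph with the Exclusion Criteria and the Meal test section: who has the OGTT, at which visits, and what preload a subject without it receives. The clinical rule itself is for the investigators.
2. Report OGTTs not done by arm, visit and reason.
3. Keep the planned repeated-measures model for 120-minute glucose. Add a prespecified sensitivity analysis that ranks subjects excluded for new diabetes as worst. Report fasting glucose and HbA1c alongside; both are scheduled for all subjects and do not need the glucose load.
4. In the buffet model, include baseline OGTT status (glucose load given or not) as a covariate, and repeat the analysis without sessions that lacked the load. Baseline status is preferable to the preload actually given at week 36, which is measured after randomization and could itself be affected by treatment.

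The cost is SAP wording and two supplementary analyses. The rank analysis gives up the mg/dL scale, and the restricted buffet analysis loses a few subjects and, if sessions are dropped for new diabetes, is no longer a fully randomized comparison. Both should therefore remain sensitivity analyses.

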Currently available GLP1RAs include a variety of schedules: twice daily (exenatide), once daily (liraglutide), and once weekly (exenatide, albiglutide, and dulaglutide). Alternatively, levels of native GLP-1 can be increased by inhibiting dipeptidyl peptidase 4 (DPP-4), a protease that rapidly degrades native GLP-1. However, DPP-4 inhibitors do not inhibit appetite or lead to body weight reduction.

Liraglutide, the active ingredient in Saxenda®, was recently approved as a weight loss medication showing a 7.3% decrease in body weight over a 56 wk trial in adults with severe obesity.^{104,105}

However, this drug has not been made available for use in pediatric studies and this is not expected to change in the near future (personal communication with Medical Director, Obesity at Novo Nordisk Inc). Therefore, we decided to use the extended-release GLP-1 receptor agonist ExQW which is also advantageous as it requires only weekly injections, addressing some of the adherence and side effect issues that could pose barriers to therapy. This drug contains exenatide, which is a 39-amino-acid synthetic version of exendin-4 that shares approximately 50% sequence identity with human GLP-1. In previous studies of adults with T2DM, ExQW showed slightly larger reductions in body weight compared with twice daily exenatide, although this difference was statistically not different.¹⁰⁶ Mild to moderate GI adverse events were common in previously tested three GLP-1 agonists, and were least frequent with ExQW.^{33,106-108} ExQW contains exenatide encapsulated in microspheres consisting of a medical-grade biodegradable poly-(d,l-lactide-co-glycolide) polymer, which has been used in other medical applications since 1984, and allows for slow, continuous release of the active agent into circulation following injection.^{34,109} ExQW will be started at 2 mg subcutaneously once weekly.

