Study Visits (SVs): After the initial screening visit, there will be 5 study visits (see overview and measures in **Fig. 1**) to assess adherence, drug safety, outcomes, and to distribute the drug or placebo. Hypoglycemia medications will be adjusted as needed. During the duration of the treatment, subjects with persistent abdominal pain and nausea/vomiting will discontinue study medication and be evaluated for acute pancreatitis and cholecystitis. In children, most adverse effects are mild GI effects that are transient.¹¹⁷ Subjects not tolerating their current dose will be discontinued from study at PI's discretion. Study medication will resume if and only if no significant adverse event is found and subjects concur. Subjects need to fast and refrain from exercise for ten hours prior to study visits for fasting blood draws. Physical exams including Tanner staging, and inspection of injection sites will be done at all visits (except no Tanner staging at 6 weeks visit). If a subject withdraws from the study or is withdrawn by an investigator for any reason, subjects will be asked to complete SV4 study procedures, not including the DEXA scan.

Other measures assessed at SVs (see Fig. 1):

- Questionnaires (eating, activity): SVs 1, 3, 4,
- 24h dietary recall-done the week prior to : SVs 1, 3, 4, 5
- Anthropometry: SVs 1, 2, 3, 4, 5
- Vital signs: SVs 1, 2, 3, 4, 5
- Actimetry: SVs 1, 3, 4
- Blood for metabolic outcomes: SVs 1, 3, 4, 5
- OGTT: SVs 1, 3, 4
- Energy intake at free buffet meal: SVs 1, 4
- Whole body DEXA in order to evaluate body composition: SVs 1, 4
- DLW energy balance assessment: SVs 1, 4
- ECGs: SVs 1, 3, 4, and 5
- Safety labs (electrolytes, CBC, lipase, amylase, glucose, ALT, AST, creatinine, hemoglobin A1c, and thyroid hormones): SVs 2, 3, 4, 5
 - Additional serum will be obtained at all sites and stored at a central location (SCRI Seattle) for future use (3 ml in case anti-exenatide antibodies will need to be assessed)
- CEA: SVs 3, 4, 5
- Calcitonin: SV 5
- MRI (if needed): SV 1

Weekly Contact: Research participants will be contacted weekly by telephone/email to assess for potential adverse events, concomitant medications, and compliance with dosing. Participants will also be reminded about their urine collections, diet recalls, and return of the accelerometer during these phone calls.

Visit Schedule:

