8. Discomfort, significant hyperglycemia, nausea, a reaction or sensitivity triggered by the oral dextrose solution. Discomfort, nausea, or a reaction from an unidentified food allergy or sensitivity to used study foods.
9. The DLW tracer is made up of the stable isotopes of hydrogen (^2H) and oxygen (^{18}O) and therefore does not give out harmful radiation. These stable isotopes are found naturally in our drinking water and in our bodies. These isotopes have been used extensively to measure body composition and energy expenditure in premature infants, newborns, toddlers, children, adolescents, and pregnant and lactating women with no adverse effects. The deuterium oxide has been used across the world to measure human breast milk intakes in infants from newborns to 12 months of age. The DLW tracer in fact is cleaner than any tap water and fountain water.
10. Risks associated with the study drug. In this proposed study, subjects will receive weekly subcutaneous injections of placebo or ExQW 2 mg starting at week 0. ExQW may hurt an unborn child. It can change the way warfarin is metabolized. Exenatide is FDA approved for treatment of people with diabetes. Because the treatment in this study is investigational, there may be risks that we do not know about at this time.

In a recent multicenter study including 461 adults with T2DM treated with ExQW for 26 weeks, 61% of patients had one or more adverse events (AEs).³¹ Related to 461 patients, most frequent were injection site reactions (10% injection-site nodule, 4% subcutaneous nodule, 3% injection-site pruritus, 3% nodule, 2% injection-site erythema), followed by 9% developed nausea, 7% nasopharyngitis, 6% diarrhea, 6% headache, 5% decreased appetite, 5% constipation, 4% vomiting, 3% dizziness, 3% upper respiratory-tract infection, 3% abdominal pain, 2% dyspepsia, 2% unexpected therapeutic response, and 2% bronchitis. These results were similar to another clinical trial of adults with T2DM treated with ExQW up to 2 years.³⁷ Here 80% of subjects reported at least one AE, most frequently nausea (17%), injection site nodule (12%) and nasopharyngitis (12%). Overall expected AEs associated with the GLP-1 agonist ExQW may include:

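### The SAE definition has no congenital-anomaly or medically-important-event item, and the one-day DMC rule otherwise rests on an undefined dose-limiting toxicity, so harms the protocol names are not reliably expedited

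*Combined protocol and SAP*

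**What the plan says.** Section 7, Investigator Oversight Responsibilities, routes SAEs and dose-limiting toxicities to both the independent DMC and the IRB, under a separate safety plan. Monitoring Procedures then sets the clock: "Serious adverse events and dose-limiting toxicities are submitted within one day of learning of the event to the IDMC".

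Under Collection and Reporting of SAEs and AEs, the protocol presents the definitions in use for this study. It gives two, for AE and SAE. The second begins "Serious Adverse Event: Any AE that results in any of the following outcomes" and lists four outcomes: death, threat to life, inpatient admission or a prolonged stay, and lasting or significant disability. The list ends there.

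Two other routes to the DMC appear in Section 7. Under Emergency Unblinding, drug-related SAEs and treatment-emergent adverse events (TEAEs) lead to immediate contact with the Principal Investigators, who contact the DMC and consider breaking the blind. Separately, the study statistician sends the DMC semi-annual reports that include aggregate AEs and safety laboratory results.

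On dosing, Section 4 (Rationale for Medication) says "ExQW will be started at 2 mg subcutaneously once weekly", and Section 7 says "subjects will receive weekly subcutaneous injections of placebo or ExQW 2 mg starting at week 0". On intolerance, Section 6 says "Subjects not tolerating their current dose will be discontinued from study at PI's discretion".

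Among the risks, Section 7 states "ExQW may hurt an unborn child". It also describes pancreatitis, and a boxed warning on thyroid C-cell tumors with calcitonin kept as a safety measure. Section 6 stops the drug and requires a work-up when symptoms suggest pancreatitis or cholecystitis.

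**The concern.** Expedited reporting works only if the person who learns of an event can tell from the text whether it qualifies. Here the two triggers are the SAE list and dose-limiting toxicity. The list omits the two categories under which the drug-specific harms named in this protocol would most naturally fall when there is no admission. The second trigger borrows a term that normally supports a decision about dose level, in a trial that describes one level.

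At stake is whether the DMC hears promptly, and on the same basis from all three sites, about the harms for which the protocol itself excludes patients, stops drug or draws safety samples.

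**Working it through.** No sample-size, power or event figure is involved, so the check sets the passages side by side.

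**1. Named harms against each trigger.** The SAE column applies the four outcomes as written. The third column tries the most natural meaning of dose-limiting in a one-dose trial, namely toxicity that stops the drug.

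| Harm named in the protocol | SAE on the four-item list? | Dose-limiting, if that means the drug is stopped? | Emergency Unblinding route? |
|---|---|---|---|
| Pancreatitis managed without admission | No | Probably yes, since Section 6 stops drug on suspicion; unclear if drug is later resumed | Yes on an ordinary reading |
| C-cell or thyroid tumor found in clinic, before any admission | No | Unclear; calcitonin after screening is listed only at study visit 5, the end of treatment, when there may be no drug left to stop | Yes on an ordinary reading |
| Fetal anomaly | No | No clear answer | Unclear; not obviously an event in the participant |

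With a congenital-anomaly item and a medically-important-event item that names pancreatitis and C-cell or thyroid tumor, all three rows would become SAEs. The one-day rule would then apply without recourse to the other columns.

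**2. The term dose-limiting toxicity.**
- Uses: four, all in Section 7 (once in the oversight paragraph, once in the one-day sentence, twice in the descriptions of the semi-annual reports).
- Definitions in this document: none.
- Dose levels described: one, 2 mg weekly. No cohort, escalation or reduction step is described, and intolerance leads to discontinuation.

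The term can therefore attach only to stopping drug. The text does not say so. Nor does it say whether the temporary stop in Section 6, with possible resumption, counts.

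**3. The timings.** Three stand next to one another: one day (SAE or dose-limiting toxicity), immediate (drug-related SAE and TEAE), and semi-annual (aggregate AEs). TEAE is not defined, and it is unclear whether drug-related qualifies TEAE or only SAE.
- Read broadly, every TEAE, mild nausea included, goes to the DMC immediately, ahead of a death judged unrelated, which has one day.
- Read narrowly, the paragraph is a procedure for deciding whether to unblind, not a reporting rule. It then fits poorly with the 18-week extension, in which everyone openly receives ExQW.

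**4. What is deferred.** Section 7 sends the details of AE monitoring and DMC reporting to the separate safety plan, along with AE grading, attribution and management. It does not send the SAE definition there. The four-item list is the stated rule.

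**The case against.** The strongest reply is that other routes already reach the DMC. Pancreatitis or a C-cell tumor arising on drug would ordinarily be a TEAE, and the Emergency Unblinding paragraph calls for immediate contact. If dose-limiting means that drug is stopped, suspected pancreatitis is already a one-day event. The safety plan, which is not among the documents, may define the term or list events of special interest. Investigators also review all AEs in real time, expedited reports go through one REDCap system, and weekly contacts ask about AEs and dosing. The fetal case is remote: pregnancy is excluded and tested for at screening, and sexually active female participants must use birth control unless gonadotropin deficiency is documented.

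Much of this stands, and it limits the finding. A reader might infer that the named harms need not be expedited, or that they would wait for the next semi-annual report, about 26 weeks (52/2). The documents do not support that. The wait would arise only if an event met neither one-day trigger, the TEAE route was not used and the safety plan added nothing. A reader might also use the protocol's nausea and vomiting rates to size the problem, but those rates count events, not missed or late reports, and no stopping rate is given. Uneven reporting between sites is possible but not shown.

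The reply does not repair the SAE list, which is stated here and not deferred. Nor does it align the Emergency Unblinding paragraph with the one-day sentence.

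**Conclusion.** The point holds as a gap in classification and an unaligned set of triggers. Two categories are missing from a stated four-item definition. One of the two one-day triggers is undefined in this document and has no dose step to refer to. Three timings for the DMC are not reconciled. As a result, non-admitted pancreatitis, a C-cell tumor found in clinic and a fetal anomaly are not SAEs on the list as written, and their submission within one day is not assured. They are not excluded from reaching the DMC, and no length of delay or number of affected participants can be derived from these documents.

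This rests on two assumptions: that sites apply the SAE list as printed, and that the unseen safety plan does not restate it. If that plan defines dose-limiting toxicity or lists special events, the second and third parts reduce to a missing cross-reference. The protocol's own SAE list would still need correcting.

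**What to change.** 1. In Section 7, add to the SAE list congenital anomaly or birth defect, and medically important events, naming pancreatitis and C-cell or thyroid tumor as examples.
2. Define dose-limiting toxicity for a one-dose design, including whether a temporary stop counts, or cite the exact section of the safety plan that defines it. Whether every drug interruption deserves one-day reporting is a trade-off for the sponsor and the DMC; this point does not require it.
3. Reconcile the one-day sentence with the Emergency Unblinding paragraph: define TEAE, say whether drug-related qualifies it, say whether the paragraph is a reporting rule or only an unblinding procedure, and say whether it applies in the open-label extension.

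The cost is wording in the protocol, matched in the safety plan and the REDCap SAE form, plus a few more expedited reports. No visit, test, dose or treatment rule changes.
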